This project is theoretically innovative because it conceptualizes prenatal depressive symptoms and cannabis use as key factors for tobacco use during pregnancy and in the postpartum. Moreover, it frames that research question in the context of intersecting identities and experiences that may promote tobacco use before, during, and after pregnancy and hamper cessation efforts, contributing to lapse and relapse. It is methodologically innovative to elevate the voices of those with lived experiences of depressive symptoms, tobacco, and cannabis use to co-develop an intervention for prenatal tobacco cessation with real world impact. Human centered design (HCD) and IM are powerful methods to translate community perspectives into workable solutions for pregnant people who smoke. Demonstrating the importance of addressing depressive symptoms and cannabis use for success in prenatal smoking cessation also has significant implications for clinical practice. Collaboratively developing an intervention will enable us to design an intervention that incorporates minoritized people’s views and lived experiences of depression, stress, discrimination, stigma, trauma and other contexts in a way that is distinct from previous “one-size fits most” approaches in other prenatal substance use interventions. Members from minoritized groups will adapt intervention parameters that address their needs, contexts that should be emphasized, and which elements are less relevant to their circumstances.

D2. Preliminary results

The investigative team has conducted prior research examining health disparities in

prenatal substance use as well as relations among prenatal depressive symptoms, cannabis use and tobacco use. Most participants in the YoungMoms project are Black or Biracial (78%) and one-third identify as something other than strictly heterosexual (21% are bisexual). As seen in Figure 2, sexual minority (SM) participants in the YoungMoms study are more likely to smoke during pregnancy compared to those who identified as heterosexual ([name] et al., under review). In qualitative interviews, some SM participants linked their experiences as a SM and related mental health with prenatal tobacco use. The results of this and other research (e.g., Beck et al., 2021; Gonzalez et al., 2019; King et al., 2020) demonstrate that pregnant SM people need to be included in research related to prenatal tobacco and cannabis use.

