Relatedly, we examined the effectiveness of two postpartum smoking relapse preventions as a function of prenatal depressive symptoms ([name] et al., 2020). People with clinically significant depressive symptoms late in pregnancy did not maintain smoking abstinence in the postpartum if they received a standard intervention with behavioral techniques to manage cigarette cravings (SUPPORT). However, as seen in Figure 3, those who were depressed late in pregnancy were more successful maintaining abstinence if they received a smoking abstinence intervention that was tailored to psychosocial factors such as mood (STARTS). These results highlight the importance of depressive symptomatology in postpartum tobacco abstinence and the significance of addressing prenatal depressive symptoms for long-term impact on maternal and child health. Thus, we propose to

invite people who use tobacco and cannabis and experienced elevated depressive symptoms during pregnancy to partner with us in an intervention development project to reduce tobacco-related health inequities.

Study Design

1. Total number of subjects to be enrolled at this site (enter -1 for chart reviews, banking, registries):

25

2. Describe and explain the study design:

This study is an experimental, single-arm feasibility trial.

3. Describe the primary and secondary study endpoints:

The primary outcomes of the trial is the feasibility and acceptability of the novel intervention and abstinence from tobacco and cannabis use. Feasibility and acceptability of the intervention will be assessed using attendance, completion of intervention-related procedures, and the Acceptability of Intervention Measure (AIM). Abstinence will be measured by proportion of the participants who self-report no use of either substance and by calculating the proportion of participants with negative urine screens for THC and COT. Secondary outcomes include changes in depressive symptoms, tobacco, and cannabis use from the baseline assessment in pregnancy to 3 months postpartum.

4. Provide a description of the following study timelines:

Duration of an individual subject's active participation:

Depending on gestation age at enrollment, subjects will actively participate in the study for approximately 6 to 12 months.

Duration anticipated to enroll all subjects:

9/30/2026

Estimated date for the investigator to complete this study (complete primary analyses):

10/1/2027

5. List the inclusion criteria:

- (1) <26 weeks of gestation

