*** Identify the subgroups and provide a justification:**

We exclude individuals under age 18 from this work because the perinatal concerns and treatments for depression of individuals younger than age 18 are likely to differ from those of individuals 18 years of age or older and would require developmentally appropriate assessments and interventions.

8. Describe the power analysis used and cite your method of statistical analysis. If a power analysis is not possible, thoroughly justify the sample size required for the study, including appropriate literature citation (alternatively provide page reference in attached protocol):

Chi-square tests will be used to calculate differences in feasibility as a function of key intersecting identities (e.g., age, race, ethnicity, SM status) and use history variables. If feasibility is found to be significantly different by race or SM status, the analyses will be weighted to account for differences in attrition. We will assess the preliminary efficacy of the novel intervention to promote self-reported abstinence from tobacco and cannabis at the end of pregnancy (Time 3) and 12-16 weeks postpartum (Time 4). The proportion of self-reported abstinence among participants in the INT and EUC groups at Times 3 and 4 will be compared using chi-square tests of difference. We will stratify by race and sexual orientation to test for intersectional effects. Secondary analysis will examine differences in biochemically verified abstinence (urine dip test for presence of cotinine or THC) and depressive symptoms between INT and EUC using chi square tests and compare depressive symptoms (EPDS) scores in the two groups using two-sample t-tests. The Cochran Q test will be applied to self-reported tobacco and cannabis use across the 4 time points within the INT group to test whether there has been a change in the ratings over time. Next, a generalized linear mixed effects model (GLMM) with a logit link will be used to test the treatment effect (INT vs. EUC) and treatment by time interaction to test whether the rate of abstinence over time was steeper among the INT group compared to the EUC group. We have 70% power to detect a 15% difference in quit rates between INT and EUC, assuming a 25% intervention arm quit rate and 10% control arm quit rate.

Pregnant Women

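### Chi-square tests for feasibility by subgroup are unreliable in 25 people: where the smaller group has 5 or fewer, one person missing the attendance threshold can give p<0.05 and, for race, trigger weighting

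*Protocol*

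**What the plan says.** The protocol describes the design thus: "This study is an experimental, single-arm feasibility trial". The entry beside "Total number of subjects to be enrolled at this site" (Study Design, item 1) is 25.

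Study Aims, item 1 defines feasibility by attendance at more than 4 sessions and says it will be compared by demographic and use-history variables. Study Design, item 8 names the test: "Chi-square tests will be used to calculate differences in feasibility as a function of key intersecting identities". Its list covers age, race, ethnicity, SM status and use history. The number of categories per variable and the significance level are not given, and no alternative is named for sparse tables.

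The same item attaches a consequence: "If feasibility is found to be significantly different by race or SM status, the analyses will be weighted to account for differences in attrition".

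The only guide to subgroup sizes is the team's earlier cohort, in D2. Preliminary results: "Most participants in the YoungMoms project are Black or Biracial (78%) and one-third identify as something other than strictly heterosexual", of whom 21% overall are bisexual. The trial sets no subgroup targets.

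**The concern.** The Pearson chi-square test takes its p-value from a large-sample distribution. The usual working rule asks for expected counts of at least 5. In 25 people with most of them attending, the expected number missing the threshold in a small group is a fraction of one person, and the approximation can be badly off.

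Two things are at stake. A difference resting on one person could be reported as a significant racial or ethnic difference in engagement, in a project centred on such inequities. For race, and for SM status if that group is small enough, the result also decides whether the analyses are weighted. The protocol itself names the test, so this is a stated choice and not a detail left open.

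**Working it through.** **Inputs.** N = 25 (Study Design, item 1); one arm (item 2); chi-square tests and the weighting trigger (item 8); threshold of more than 4 sessions (Study Aims, item 1). Assumed: two-sided 5% level, no continuity correction, and subgroup sizes. Applying the earlier cohort's shares to 25 gives 0.78 × 25 = 19.5 vs 5.5 for race and 25/3 = 8.3 vs 16.7 for SM status. Item 8 states no figure for these tests, so there is nothing of its own to reproduce. Its one power statement concerns quit rates between two arms.

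**Expected counts.** If at least 70% of participants meet the threshold (an assumption), at most 7 of 25 miss it. The smallest expected count in any two-by-two table is then at most 12 × 7/25 = 3.36, below 5 for every split. With one person missing it and a 5 vs 20 split, it is 5 × 1/25 = 0.2.

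**One person missing the threshold, in the smaller group of size m, none in the larger.** The Pearson statistic reduces to 25(25 − m)/(24m), and the Fisher p-value is m/25.

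| Split | Pearson p | Fisher p |
|---|---|---|
| 1 vs 24 | <0.0001 | 0.04 |
| 2 vs 23 | 0.0005 | 0.08 |
| 3 vs 22 | 0.006 | 0.12 |
| 4 vs 21 | 0.019 | 0.16 |
| 5 vs 20 | 0.041 | 0.20 |
| 6 vs 19 | 0.069 | 0.24 |
| 8 vs 17 | 0.14 | 0.32 |

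For m = 5 the statistic is 25 × 20/120 = 4.17. The 5% critical value is 3.84, so m must be 5 or less.

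**A one-person category whose member misses the threshold, with F people missing it overall.** The statistic is 25(25 − F)/(24F) and Fisher p = F/25. At F = 5 these are 4.17 (p = 0.041) and 0.20. Pearson is therefore significant for any F up to 5.

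**Type I error of the uncorrected Pearson test at nominal 5%.** All tables were enumerated under a common attendance probability.

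| Split | Attendance | Type I error |
|---|---|---|
| 5 vs 20 | 70–85% | 4.3–5.8% |
| 5 vs 20 | 90%; 95% | 7.6%; 9.0% |
| 1 vs 24 | 80–90% | 9–11% |
| 21/3/1 | 85%; 90% | 8.8%; 10.6% |
| 19/4/1/1 | 85%; 90% | 10.5%; 12.5% |
| 6 vs 19 | 70–95% | 1.4–4.6% |
| 8 vs 17 | 70–95% | 2.6–5.1% |

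The fully exact test stayed at or below 3.3% in every one of these splits.

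**The case against.** The strongest reply is that the problem is confined to particular tables, and much of that stands.

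- A reader might infer that one non-attender could produce a significant SM difference. At the earlier cohort's one-third share the split is about 8 vs 17, where one gives p = 0.14. Two are needed (2/8 vs 0/17: Pearson 0.032, Fisher 0.093).
- Race sits on the boundary. A share of 22% of 25 is 5.5 people; at 6 vs 19 one person gives p = 0.069 and the error rate is at most 4.6%.
- The 5 vs 20 example needs 24 of 25 to meet the threshold, with the one failure in the small group. With no true difference its probability is 5 × 0.1 × 0.9^24 = 4.0% at 90% attendance and 0.5% at 80%. One further failure in the larger group (1/5 vs 1/20) gives p = 0.27.
- The result assumes an uncorrected test. With Yates correction, one person is significant only in a one-person group (p = 0.017).
- A reader might also infer that every later analysis would change materially. The protocol says only that the analyses will be weighted, and the effect may be small. If the one non-attender of 5 is also lost to follow-up, the other four get weight 5/4 = 1.25 and that group's share moves from 4/24 (16.7%) to 20%. An overall proportion then shifts by 0.7 points if the groups differ by 20 points.
- Changing the test leaves the weighting dependent on a significance test.

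These points limit the concern without removing it. Race or ethnicity recorded in several categories can readily leave groups of 1 to 4 in 25 people, and item 8 has no rule for them.

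**Conclusion.** The concern holds in a limited form. Where the smaller group has 5 or fewer people, which is plausible for race or ethnicity and for SM status only if that group is so small, the named test can call one person's attendance significant when the exact p-value is 0.08 to 0.20 (groups of 2 to 5). For race this can trigger weighting. Type I error can reach about 8 to 12% for 5 vs 20 at 90% attendance or more, or in tables with one-person categories.

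The documents do not support saying that the error rate is wrong in all these comparisons: at 6 vs 19 and 8 vs 17 it is near or below nominal. The subgroup sizes, the 5% level and the uncorrected form of the test are all assumptions. This is a worthwhile correction to a stated method, of moderate weight.

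**What to change.** In Study Design, item 8, replace chi-square for the feasibility comparisons with the fully exact test conditional on the margins: Fisher for two groups, Fisher-Freeman-Halton for more. State that the same test decides whether feasibility differs by race or SM status for the weighting rule. Report each group's count meeting the threshold with an exact confidence interval.

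Do not use the mid-p version. For one non-attender it halves the exact p-value, giving 0.04/2 = 0.02 in a group of 1 and 0.08/2 = 0.04 in a group of 2, so it would still flag one person in either.

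The cost is a line of text and a software option. The exact test is conservative here (size about 0 to 3%), so fewer differences will be called significant. A one-person group can still reach p = 0.04 when its member is the only one to miss the threshold.

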In addition to the incentive for completing assessments, we have budgeted up to \$50 for a clean (i.e., no evidence of tobacco and cannabis use) sample as a contingency management incentive at the final postpartum assessment (T4).

Participants will be paid using Vincent, the University's approved payment system. There will be no compensation for partial completion of T1, T2, or T3. At T4, participants will be paid separately for completing all questionnaires (\$75) and interviews (\$25).

5. Recruitment materials: (attach all material to be seen or heard by subjects, including advertisements and scripts)

	Document	Category	Date Modified	Document History
View	Recruitment Scripts(1)	Recruitment Materials	2/3/2026	History
View	Intervention Screening Survey(2)	Recruitment Materials	1/30/2026	History
View	Recruitment flyer(1)	Recruitment Materials	1/6/2026	History

Study Aims

1. * Describe the purpose, specific aims, or objectives and state the hypotheses to be tested:

Guided by the PICTURe community collaborative, we will conduct a single group, proof-of-concept feasibility trial of a new intervention designed to address prenatal depressive symptoms to encourage tobacco and cannabis cessation. We will examine the initial feasibility and acceptability of the intervention using standard measures in addition to measures suggested by the collaborative. We hypothesize that 1) the intervention will be feasible to participants and 2) the intervention will be acceptable to participants.

The primary outcomes of the trial are the feasibility and acceptability of the novel intervention and abstinence from tobacco and cannabis use. Feasibility and acceptability of the intervention will be assessed using attendance, completion of intervention-related procedures, and the Acceptability of Intervention Measure (AIM). Abstinence will be measured by proportion of the participants who self-report no use of either substance and by calculating the proportion of participants with negative urine screens for THC and COT. Secondary outcomes include changes in depressive symptoms, tobacco, and cannabis use from the baseline assessment in pregnancy to 3 months postpartum.

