De-identified data from the project will be saved in a database prepared for the study. The database will be password protected. The MPIs will make deidentified data collected from research participants available to other researchers and community partners after the study is completed and the final report has been generated. Data will be provided in the form of Excel files containing only ID codes as subject identifiers. No identifying information, including names, telephone numbers, or addresses, will be made available. Researchers requesting use of data must submit their request in writing to the MPIs, including the purpose for which they are requesting use of the data. These requests will be reviewed by the Investigators and will require engaging in a Data Use Agreement (DUA), in cooperation with the University of Pittsburgh. Data will be of sufficient quality to allow other investigators to validate and replicate research findings, consistent with NOT-OD-21-013. Updates on data sharing activities will be provided in annual progress reports to the funding organization.

- 3. If any research data is collected, stored, or shared in a paper format, address what precautions will be used to maintain the confidentiality of the data:**

Paper documents are kept in locked filing cabinets in an office of the Western Psychiatric Hospital at the University of Pittsburgh. Access to subject data records will be given only to the PI and study staff supervised by Drs [name] and [name].

Specimens and Related Data

1. * Data and Specimens will be stored:

Limited time (i.e., only until the study is completed)

2. * Indicate the type of specimen, describe where stored, and for how long:

Participants will be asked to provide one urine sample during their final assessment.

The sample will be tested for cotinine and THC and then disposed of immediately after this testing.

3. * How the specimens will be accessed and who will have access to the specimens:

The urine sample will be collected by the participant and accessed only by the research staff testing the sample.

4. * List the data to be stored or associated with each specimen:

The results of the THC and cotinine dip tests, date and time of the test, participant ID number, and documentation of payment for negative results will be recorded in a secure study database.

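### The protocol does not fix which abstinence measure, at which time point, is the primary abstinence result: urine is primary in the aims and endpoints but secondary in the analysis text

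*Protocol*

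**What the plan says.** **Role in the aims and endpoints.** Protocol, Study Aims item 1: "The primary outcomes of the trial are the feasibility and acceptability of the novel intervention and abstinence from tobacco and cannabis use". Study Design item 3 repeats this almost word for word. Both places give two measures. The first is the share of participants whose own report is of no tobacco and no cannabis use. The second is a urine measure, obtained by "calculating the proportion of participants with negative urine screens for THC and COT". Neither measure is ranked above the other, and neither has a time point. The secondary outcomes listed in both places are changes in depressive symptoms and in tobacco and cannabis use. Urine-verified abstinence is not among them.

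**Role in the analysis.** Study Design item 8 starts with self-reported abstinence at Times 3 and 4, and then states: "Secondary analysis will examine differences in biochemically verified abstinence (urine dip test for presence of cotinine or THC"). Both analyses compare an INT group with an EUC group. Study Design items 1 and 2 describe one arm of 25 participants.

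**Timing.** Item 8 equates Time 3 with the close of pregnancy and Time 4 with 12 to 16 weeks postpartum. Recruitment Methods item 4 and Research Activities item 1 put T3 at one month postpartum. The late-pregnancy assessment there is T2, at 32 to 36 weeks' gestation. Urine is taken once. Specimens and Related Data item 2: "Participants will be asked to provide one urine sample during their final assessment", that is, at T4.

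**The concern.** The same measure is primary in two sections and secondary in a third. Someone who writes the report from the endpoint section would present two primary abstinence rates. Someone who writes it from item 8 would present one, by self-report, at two times, one of which is labelled inconsistently with the schedule.

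A participant who reports no use but has a positive dip test at T4 counts as abstinent on one measure and not on the other. The abstinence rate that readers take away, and that may be used to plan a later trial, then depends on which section is followed. The feasibility and acceptability results are not affected.

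**Working it through.** **1. The plan's own figure.** Item 8 claims 70% power for quit rates of 25% against 10%, without saying which abstinence measure these rates refer to. It states no alpha, sidedness or group size. With a two-sided alpha of 0.05 (assumed), the normal approximation with pooled variance is

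power = Φ[(0.15·√n − 1.96·√(2·0.175·0.825)) / √(0.25·0.75 + 0.10·0.90)], with n per group.

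- n = 12.5 (25 split equally): (0.530 − 1.053)/0.527 = −0.99, power 16%.
- n = 25 per group: (0.750 − 1.053)/0.527 = −0.58, power 28%.
- 70% power needs 79 per group.

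The figure does not reproduce with 25 participants. It also belongs to a two-group comparison that this trial does not have. That is a separate defect. It matters here only because the power statement cannot be used to infer which abstinence measure leads.

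**2. The sections side by side.**

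| Section | Self-report | Urine | Time point |
|---|---|---|---|
| Study Aims item 1 | primary | primary | none given |
| Study Design item 3 | primary | primary | none given |
| Study Design item 8 | leads | secondary | self-report at Times 3 and 4; Time 3 placed in late pregnancy |
| Research Activities item 1 | use questionnaires at T1 to T4 | T4 only | T3 at one month postpartum |

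Under the first two rows, four results could be called the primary abstinence rate: self-report at T2, T3 or T4, and urine at T4 (3 + 1 = 4). Item 8 narrows this to self-report at two times, but contradicts the first two rows on urine and the last row on Time 3.

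**3. How far the measures can part at T4 (illustration).** The documents give no discordance rate, so the inputs are assumed: 25 enrolled, all with both measures, 10 self-reporting no use (10/25 = 40%), and a share f of those 10 testing positive.

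Verified rate = 10·(1 − f)/25.

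- f = 0.10: 9/25 = 36%, a difference of 4 percentage points.
- f = 0.30: 7/25 = 28%, a difference of 12 points.
- f = 0.50: 5/25 = 20%, a difference of 20 points.

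This is the rate that requires both conditions. The endpoint section's urine measure is negative urine alone. It could also count someone who reports use but tests negative, so it need not equal the verified rate.

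**4. Precision.** The exact (Clopper-Pearson) 95% limits are the 0.025 quantile of Beta(x, n − x + 1) and the 0.975 quantile of Beta(x + 1, n − x). With n = 25:

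- 10/25: 21.1% to 61.3%.
- 9/25: 18.0% to 57.5%.
- 5/25: 6.8% to 40.7%.

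These widths reflect the sample size, not the choice of measure. They are a reason to report whichever rate leads with its interval.

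**The case against.** The strongest reply is that the urine label sits in a passage that must be rewritten anyway. Item 8 is built around an EUC group that does not exist here, so the mismatch may be a by-product of that text. This is largely right about the cause, and the two corrections should be made together. But deleting EUC would not by itself say whether urine is primary, or at what time abstinence is judged.

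Four stronger readings are tempting, and the protocol does not support them:

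- *A reader might infer that the favourable rate can be picked after the fact.* Both measures are prespecified, and dropping one would be visible. The text leaves open which one leads. It shows nothing about intent.
- *A reader might infer that the lack of a rule for discordant or missing urine results is itself an error.* Such rules commonly sit in a statistical analysis plan, and that document is not at hand.
- *A reader might infer that abstinence cannot be primary because the hypotheses cover only feasibility and acceptability* ("We hypothesize that 1) the intervention will be feasible to participants and 2) the intervention will be acceptable to participants") *and because 25 participants are few.* A proof-of-concept trial may report a descriptive primary proportion without a hypothesis or threshold.
- *A reader might infer that urine at T4 only is a flaw.* It is stated consistently, and nothing promises verification at another time.

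**Conclusion.** The point holds as a contradiction within the protocol. Negative urine has two different roles, the endpoint sections give abstinence no time point, and item 8's Time 3 does not match the schedule. An unseen analysis plan would not cure this, because the protocol itself assigns the conflicting roles.

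The size can only be illustrated. With 10 of 25 self-reporting abstinence and 10% to 50% of them urine-positive, all assumed, the verified rate is 4 to 20 percentage points below the self-reported 40%. Discordance can be seen only at T4, where both measures exist. The defect should be corrected before outcome data are seen. It concerns how abstinence is defined and reported, not the feasibility question.

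**What to change.** 1. Give abstinence the same role in Study Aims item 1 and Study Design items 3 and 8. Whether that role is primary or secondary is for the sponsor to decide.
2. Name one lead measure and time point: verified abstinence at T4, meaning self-report of no use of either substance and a dip test negative for both cotinine and THC. Report it as a single-arm proportion of all enrolled with an exact 95% confidence interval, counting missing as not abstinent.
3. Report self-report alone at T2 to T4 as supportive, and cross-tabulate self-report against urine at T4.
4. Reconcile item 8's Time 3 label with the assessment schedule.
5. Make these changes together with removal of the EUC comparison. State that item 8's conditional weighting for attrition does not apply to the lead measure, since all enrolled participants are already in its denominator.

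Cost: no new data are needed. Items 1 and 3 need only wording changes, but item 8 needs a real rewrite. Any matching registry entry, which was not seen, should follow. The stated abstinence rate becomes more conservative, because discordant and missing results both count against abstinence.

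### The secondary outcome is change in tobacco and cannabis use from baseline to 3 months postpartum, but its metric is undefined and none of item 8's use analyses, all yes/no, estimates that change

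*Protocol*

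**What the plan says.** Study Aims item 1 and Study Design item 3 separate two outcomes. Abstinence is primary, as the proportion reporting no use of either substance and the proportion with negative urine screens. Then: "Secondary outcomes include changes in depressive symptoms, tobacco, and cannabis use from the baseline assessment in pregnancy to 3 months postpartum". Neither place gives a unit, a frequency or a look-back period for use.

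Study Design item 8 lists four analyses of use:

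- Chi-square tests of self-reported abstinence at Times 3 and 4, between groups called INT and EUC.
- A comparison of urine-dip abstinence between the same groups.
- "The Cochran Q test will be applied to self-reported tobacco and cannabis use across the 4 time points within the INT group", the purpose being "to test whether there has been a change in the ratings over time".
- A mixed model for abstinence: "a generalized linear mixed effects model (GLMM) with a logit link will be used to test the treatment effect (INT vs. EUC"), together with a treatment-by-time interaction.

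Research Activities item 1 schedules a Smoking and Alcohol Use Questionnaire and a Cannabis Use Questionnaire at each of T1 to T4, and lists the Timeline Follow-back at T4 only. The list of forms in Research Activities item 2 shows two cannabis questionnaires, one for T1 and another for T2 to T4. Their contents are not shown. The inclusion criteria admit people who stopped either substance before enrolment, provided they used it during pregnancy or in the 3 months before.

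**The concern.** A change from baseline to 3 months is a within-person contrast between two visits. Item 8 offers no estimate of it. The chi-square tests have no baseline. The urine test is done once, at T4. The mixed model is aimed at a treatment effect. Cochran's Q does contain both T1 and T4, but asks only whether the proportion using differs anywhere among four visits.

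Scale is the second problem. Cochran's Q needs two-level data, so it cannot test a change in anything properly called a rating. If use is collapsed to any/none, a participant who goes from daily to weekly use counts as unchanged. If it is not collapsed, the named test cannot be run.

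At stake is the answer to a stated secondary question in a study whose title speaks of reducing use. Under item 8 as written, a reduction short of quitting is invisible to every named test, and a temporary change that has vanished by T4 can come out as a significant result.

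**Working it through.** **The plan's own figure.** Item 8 gives one computed figure: "We have 70% power to detect a 15% difference in quit rates between INT and EUC", from quit rates of 25% and 10%. It concerns a two-group comparison and does not bear on this point. It is also not reproducible with the 25 participants planned. At an assumed alpha of 0.05, two-sided, a 12/13 split gives 16.5% power and 25 per arm gives 28.2%; 70% needs 79 per arm.

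**Does each use analysis address the stated outcome?** Visit labels follow Research Activities, where T3 is 1 month postpartum. Item 8 describes Time 3 as the end of pregnancy, a separate mismatch.

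| Analysis in item 8 | Scale | Uses T1? | Uses T4? | Estimates T4 versus T1 within person? |
|---|---|---|---|---|
| Chi-square, self-report | yes/no | no | yes | no |
| Urine dip | yes/no | no | yes | no |
| Cochran's Q | yes/no | yes | yes | no, omnibus |
| Logit mixed model | yes/no | not stated | not stated | no, treatment and interaction |

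**How Cochran's Q behaves.** With k visits, column totals C (users at each visit) and row totals R (visits with use per person),

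Q = (k − 1)[k ΣC² − (ΣC)²] / (k ΣR − ΣR²), on k − 1 df.

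Take n = 25 (Study Design item 1) and k = 4. Both patterns below are constructed.

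1. *All 25 use at every visit and all cut down.* C = 25, 25, 25, 25 and every R = 4. Numerator: 3 × (4 × 2,500 − 100²) = 0. Denominator: 4 × 100 − 25 × 16 = 0. Q is 0/0 whatever the size of the reduction.

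2. *Eight abstain at T2 and T3 and use again at T4; 17 use throughout.* C = 25, 17, 17, 25; ΣC = 84; ΣC² = 1,828. Numerator: 3 × (4 × 1,828 − 84²) = 3 × 256 = 768. Denominator: ΣR = 17 × 4 + 8 × 2 = 84 and ΣR² = 17 × 16 + 8 × 4 = 304, so 4 × 84 − 304 = 32. Q = 768/32 = 24.0, p = 0.000025 on 3 df. The T1-to-T4 change in use status is zero. The result does not depend on the chi-square approximation. Each of the 8 informative rows can place its two abstinent visits in 6 ways, and Q reaches its maximum of 24 only when all 8 coincide. The exact permutation p is therefore 6/6⁸ = 1/279,936, about 0.0000036.

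Pattern 2 is extreme because all eight resume. Its direction is plausible: the background (Study Aims item 2, B1) says at least 40% of those who quit smoking in pregnancy resume postpartum, mostly within 100 days of delivery.

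**Illustrative power, n = 25, alpha 0.05.** Simulated; none of the use levels comes from the protocol. Unless stated, everyone uses at T1, days of use in 30 have mean 20 and SD 8, T4 noise SD is 8, and quitters stay quit from T2.

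| Assumed scenario | Cochran's Q | Signed-rank on T4 − T1 |
|---|---|---|
| No one quits, all cut 30% | 0% | about 94% |
| 10% quit, the rest cut 30% | about 45% | about 97% |
| 25% quit, no one else changes | about 97% | about 59% |
| No one quits, all cut 30%; mean 8, SD 6, T4 noise SD 8 | 0% | about 12% |
| 30% already stopped at T1, 40% of these relapse from T3, others cut 30% | about 60% | about 25% |

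Neither test dominates. They answer different questions.

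**The case against.** The strongest reply is that the protocol never says use means an amount. Read as change in use status, a within-person binary test over T1 to T4 is at least relevant, and the exact metric is commonly left to an analysis plan. That much stands: the documents do not establish that an amount was intended. It does not rescue item 8. Even for status, an omnibus test over four visits is not the baseline-to-3-month change, as pattern 2 shows, and the sentence names ratings for a test that cannot take them.

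A reader might infer more than the documents support:

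- *That the use analyses run over the wrong visits altogether.* They do not. Cochran's Q includes T1 and T4, and the chi-square tests include T4. The fault is the absence of a T1-to-T4 contrast.
- *That the secondary outcome simply repeats the primary one.* Primary abstinence covers neither substance used, plus urine screens. Cochran's Q looks at within-person change over visits. Both are binary, but the quantities differ.
- *That the trial could not report any reduction.* Item 8 lists tests; it does not forbid describing the questionnaire data.
- *That a paired test of amount is always more powerful.* The last three rows of the power table show how far this depends on assumed inputs. Cochran's Q is the stronger test when change is mainly quitting.

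It is also fair to say that item 8 has a larger, separate fault. It compares INT with EUC although "This study is an experimental, single-arm feasibility trial", so the section needs rewriting anyway.

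**Conclusion.** The point holds as a mismatch between a stated outcome and the stated analyses. The outcome is change in use from T1 to T4 with no metric. All four use analyses are binary and none estimates that change. Cochran's Q is undefined when no one changes status, however much use falls, and can give Q = 24.0 (p = 0.000025) when T1-to-T4 change in status is zero.

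Those two results are algebra on constructed data for 25 participants and need no assumption about effect size. The power comparison does need such assumptions and is illustrative only: it rests on use levels, noise and baseline status that the protocol does not give, and mostly supposes that everyone uses at T1, which the inclusion criteria do not require. The point affects a secondary outcome of a small feasibility trial; feasibility and acceptability are untouched.

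**What to change.** In Study Design item 8:

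1. Keep the binary methods for abstinence, and delete the clause about ratings from the Cochran Q sentence.
2. Define the secondary use outcome as each participant's T4-minus-T1 change in frequency of use, separately for tobacco and for cannabis. Report the mean or median paired change with a 95% CI and a paired test such as the Wilcoxon signed-rank.
3. Take it from the use questionnaires given at both visits, not from the Timeline Follow-back, which is listed only at T4. First confirm that the T1 and T4 forms record frequency on a common scale and look-back window. This needs particular care for cannabis, where two different forms are listed.
4. If the forms do not match, report the paired T1-to-T4 change in any-use status with a CI for the difference and McNemar's test.
5. Show participants who had already stopped at T1 separately, since they can only stay abstinent or resume.

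The cost is a few sentences, a check of the forms and two more secondary results to report. No new visits are needed, and no new forms if the existing ones match. The fallback in step 4 is blunt at this size: if all changes go one way, exact McNemar gives p = 2 × 0.5⁵ = 0.0625 with five changers and 2 × 0.5⁶ = 0.031 with six. The interval should therefore carry the interpretation.
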